|---------------------------|------------------------------|----------|-------------------------------|----------|----------|----------|
| Functional Impairment     | CGI-Improvement              | 12       | -1.75 (.62)*                  | 2.81     | -9.75    | <.001    |
| Impaired ER               | EDI-Reactivity theta score   | 11       | -.49 (.67)                    | .73      | -2.40    | .037     |
| Maladaptive ER strategies | RSQ – Involuntary engagement | 11       | -11.46 (4.30)                 | 2.67     | -8.84    | <.001    |
| Depression                | PROMIS-Depression            | 11       | -7.27 (8.26)                  | .88      | -2.92    | .015     |
| Problem Behavior          | ABC-Irritability             | 11       | -5.73 (7.25)                  | .79      | -2.62    | .026     |
| Anxiety                   | PROMIS-Anxiety               | 11       | -4.46 (10.85)                 | .41      | -0.98    | .203     |

**Note.** \*For CGI-I, value represents mean change from 4, which equals no improvement; Parent report data shown

**Figure 3.** Illustrative examples of group mean change in key measures from baseline to post-treatment

Preliminary Efficacy evidence in young adults. Some of EASE’s content was informed by [name] & [name] (2017)’s ER-focused MBI open pilot that involved nine young adults with ASD age 18-25 who reported impaired ER (no cutoff on ER impairment was used). The baseline CGI-Severity scores covered the same range as the adolescent sample, though the adult sample was slightly less impaired, with a mean baseline severity (CGI-S) of 3.67 (*SD* = .71). The CGI-Improvement scores were similar to the EASE adolescent sample (2-3; *M*= 2.67; *SD*= .50). Treatment satisfaction was acceptable (*M*= 8.13; scale 1-10). In addition, seven of the nine participants had reliable improvement in impulse control, access to ER strategies, or emotional acceptance as measured on the Difficulty in Emotion Regulation Scale (Gratz & Roemer, 2004). While these results are promising, they are limited by the absence of a control group and lack of a required threshold for ER impairment to be enrolled in the study.

**Figure 4.** Individual and Mean Changes in DERS subscales

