### Secondary Outcome Measures.

[figure not shown]
**Functional/Adaptive Outcome Measures:** Our secondary functional outcome measures include: (1) The CGI, and (2) the CAFAS, both completed by a blind rater at pre- and post-treatment, and follow-up.

**Clinical Global Impression** (CGI; Guy, 1976). The CGI is comprised of 2 scales: Severity (CGI-S) and Improvement (CGI-I), each rated on a 7-point scale. The CGI-I scale was designed to measure overall symptomatic change as compared to baseline. Scores range from 1 (Very Much Improved) to 4 (Unchanged) to 7 (Very Much Worse). The CGI-I has been used in many studies over the past 3 decades, including clinical trials of treatments for ASD (e.g., RUPP, 2002). In this study, the CGI-I is used as a categorical (responder vs. non-responder) outcome measure, and will assess global functioning (including functioning in school, activities of daily living, social activities, and home). In our open trial to pilot EASE, we successfully trained three independent raters to reliably assign CGI scores and established inter-rater agreement as well, cross-site.

**Child and Adolescent Functional Assessment** (CAFAS; Hodges, 2000). The CAFAS evaluates level of impairment in day-to-day functioning. It has over 20 years of research to support its sensitivity to change and has been applied in child welfare, juvenile justice, mental health, and school systems to identify level of functioning and needs. CAFAS domains include: School, Home, Community, Behavior Towards Others, Moods/emotions, Self Harm, Substance Use, and Thinking (assessing irrational thinking). The CAFAS has been widely used, including with samples that involved children with ASD (e.g., Bishop-Fitzpatrick et al., 2015).

**Psychiatric Symptoms/Problem Behavior:** Our primary measure of psychiatric symptoms and problem behavior will be the BPRS completed by a blind rater at pre, post-, and follow-up time points. In addition, we have several parent, self, and other reporter questionnaires of specific symptoms and problem behaviors that will be completed to allow tests of convergence across multiple reporters as well as to provide the possibility to evaluate composites via structural equation modeling, depending on the primary results.

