## 1.J.a. STATISTICAL PLAN AND DATA ANALYSIS

### **Justification of sample size that is necessary to achieve the desired power**

We will enroll 80 subjects at two sites. Using small-scale pilot pre-post repeated measures data ( $n = 12$ ), we estimated the sample size to achieve the power of 0.80 for testing each hypothesis stated in the Aims 1 and 2 above from the EASE open trial. For the hypotheses to provide evidence that EASE has a differential treatment effect on ER, functional impairment, psychiatric symptoms, and problem behaviors (hypotheses 1a, 1b, 2a, 2b), Cohen's  $d$ , or standardized mean difference, ranged from small-to-medium effect size (0.41 for Anxiety) to very large (2.81 for CGI-I). The necessary sample size to detect the smallest effect size was computed as a total of 49 (per group), with a range of 4 to 28 per group for all other outcomes with larger effect sizes, and an average across measures of 17 per group. Our primary interest is in effects with at least moderate effect sizes, as they are likely to have the most real-world impact. As such, even if there was significant attrition, we should have ample power to detect the most meaningful outcomes for Aim 1 and Aim 2. To test the mediation effects (Exploratory Aim 4), we obtained the required sample size using the methodology proposed by Judd et al. (2001) and elaborated by Montoya & Hayes (2017). A necessary condition to detect mediation is that the change score for a mediator needs to be statistically significantly associated with the change score in dependent variable after controlling for the average level of the mediator. Using this framework, we found that the necessary total sample size to detect the mediation effect with power of .80 ranged from 43 to 86 (per group), where the effect size as a partial correlation in multiple linear regression ranged from large (0.44, path: Treatment  $\rightarrow$  CAMM Mindfulness  $\rightarrow$  RSQ Involuntary Disengagement) to medium (0.31, path: Treatment  $\rightarrow$  EDI reactivity  $\rightarrow$  Depression). The maximum sample size that we can feasibility ascertain for this project is 80, which gives us a chance to detect mediation processes that have large effects; accordingly, this aim is considered exploratory.

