#### **Aim 2 (Secondary Outcomes): Demonstrate that EASE results in decreased functional impairment and reduced psychiatric symptoms and problem behaviors.**

The test of secondary outcomes will mirror the approach used in Aim 1. To evaluate change in functional impairment via CGI-I (Hyp 2a), we will create a dichotomous variable of responder = 1 and non-responder = 0. This is consistent with convention for use of the CGI-I in both psychosocial and drug treatment studies, such that 1 and 2 codes (‘very much’ and ‘much improved’, respectively) are considered responders and all others are non-responders. The other primary outcome of interest for Hyp 2b will be CAFAS scores. For Hyp 2b (psychiatric symptoms and problem behaviors), we will focus first on the BPRS as this is our most stringent and ‘blinded’ test, followed by ABC-I and PROMIS depression and anxiety.

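### The 0.80 power claimed for Hyp 2a rests on a single-arm mean change in CGI-I (d = 2.81), not on the between-arm responder comparison that will be tested

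*Combined protocol and SAP*

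**What the plan says.** Under the justification of sample size (1.J.a), the plan states that "we estimated the sample size to achieve the power of 0.80 for testing each hypothesis stated in the Aims 1 and 2". The source is described as "Using small-scale pilot pre-post repeated measures data", with n = 12. The effects are presented as "evidence that EASE has a differential treatment effect on ER, functional impairment, psychiatric symptoms, and problem behaviors (hypotheses 1a, 1b, 2a, 2b", and Cohen's d "ranged from small-to-medium effect size (0.41 for Anxiety) to very large (2.81 for CGI-I". The resulting sizes are 49 per group for the smallest effect, 4 to 28 per group for the others, and an average of 17.

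The note to the pilot effect-size table in 1.F explains the CGI-I entry: "For CGI-I, value represents mean change from 4, which equals no improvement". The same section acknowledges that the pilot had no control group.

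In the trial the outcome takes a different form. Under Secondary Outcome Measures, "the CGI-I is used as a categorical (responder vs. non-responder) outcome measure". The Aim 2 analysis says "we will create a dichotomous variable of responder = 1 and non-responder = 0", with codes 1 and 2 counted as response. Hyp 2a in 1H is stated relative to the ACC group.

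**The concern.** The effect size and the planned test differ in two ways. The d is a mean on a 7-point scale, whereas the endpoint is binary. The d compares one treated group with a fixed value, whereas Hyp 2a compares two randomised arms, one of which receives supportive therapy of equal length. A standardised distance from the no-change point says nothing about the power to separate two responder rates, and no responder rate is assumed for either arm.

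The interpretation of Hyp 2a is at stake. The sizing paragraph concludes that power is ample even with significant attrition. A reader who takes d = 2.81 as the basis for Hyp 2a would read a null responder comparison as strong evidence of no functional benefit. The design may not support that reading, depending on how many ACC participants respond.

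**Working it through.** **1. Reproduce the plan's figures.** The inputs are the six d values in the pilot table of 1.F: 2.81 (CGI-I), 0.73 (EDI), 2.67 (RSQ), 0.88 (depression), 0.79 (ABC-I) and 0.41 (anxiety). The plan states no alpha or sidedness, so two-sided 0.05 is assumed. The calculation takes the smallest n for which a t-test with noncentrality d√n (one-sample or paired) or d√(n/2) (two-sample, n per group) has power of at least 0.80.

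| Test | CGI-I | EDI | RSQ | Depression | ABC-I | Anxiety | Average |
|---|---|---|---|---|---|---|---|
| One-sample/paired | 4 | 17 | 4 | 13 | 15 | 49 | 17.0 |
| Two-sample, per group | 4 | 31 | 4 | 22 | 27 | 95 | 30.5 |

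The stated 4, 49 and 17 match the one-sample row. The sizing therefore tests EASE change against a fixed value, not EASE against ACC. CGI-I alone cannot show this, because both tests give 4; the 49 and the 17 do. The stated upper end of 28 is not reproduced by any variant that also gives 49 and 17.

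**2. Confirm what 2.81 is.** From the pilot table, 1.75/0.62 = 2.82, and 2.81 × √12 = 9.73 against the reported t of 9.75. It is a one-sample effect.

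**3. Recover the pilot responder rate.** The inputs from 1.F are n = 12, mean 2.25, SD 0.62 (0.63 in the text), and every participant at least somewhat improved, so all scores are 1, 2 or 3. A mean of 2.25 allows five patterns (counts of 1/2/3):

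| Pattern | SD | Responders |
|---|---|---|
| 0/9/3 | 0.45 | 9/12 |
| 1/7/4 | 0.62 | 8/12 |
| 2/5/5 | 0.75 | 7/12 |
| 3/3/6 | 0.87 | 6/12 |
| 4/1/7 | 0.97 | 5/12 |

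Only 1/7/4 fits. It gives 1.75/0.6216 × √12 = 9.75, the reported t. The pilot responder rate is therefore 8/12 = 67%, exact 95% CI 35% to 90%.

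**4. Power for the planned comparison.** With p1 = 0.667 (EASE), p2 = the assumed ACC rate, n per arm and p̄ = (p1 + p2)/2:

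power = Φ{[(p1 − p2)√n − 1.96√(2p̄(1 − p̄))] / √(p1(1 − p1) + p2(1 − p2))}

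Example with p2 = 0.40 and n = 30: (0.267 × 5.477 − 1.96 × 0.7055)/0.6798 = 0.117, so power is 0.55.

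The arm sizes are 40 (80 randomised equally) and 30 (the plan's 25% attrition, leaving 60).

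| Assumed ACC rate | n per arm for 0.80 | Power, 40 per arm | Power, 30 per arm |
|---|---|---|---|
| 20% | 17 | 0.995 | 0.97 |
| 30% | 28 | 0.92 | 0.83 |
| 40% | 54 | 0.67 | 0.55 |
| 50% | 136 | 0.33 | 0.26 |

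The highest ACC rate that keeps power at 0.80 is about 36% with 40 per arm and about 31% with 30 per arm.

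**5. Sensitivity to the EASE rate.** If the true EASE rate is 50%, those ceilings fall to about 20.5% (40 per arm) and 16.5% (30 per arm). At 75% they rise to about 44.5% and 39.5%. Fisher's exact test is somewhat less powerful: at 67% against 40% it gives 0.61 and 0.45.

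**The case against.** Several points on the other side stand.

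- **CGI-I did not set the sample size.** The plan describes 80 as the most it can feasibly recruit and argues from effects of at least moderate size. Nor does CGI-I alone fix the bottom of the range: RSQ, with d = 2.67, also gives 4.
- **Low power is not shown.** A reader might infer that 80 participants are too few. The documents do not support that, because they give no ACC responder rate. At 20% to 30% the design has power of 0.83 or more in either scenario.
- **CGI-I is not singled out.** A reader might take Hyp 2a to be the best-powered outcome, or the only blinded functional one. The plan says neither. CAFAS is also completed by the blind rater, and the Aim 2 analysis treats the BPRS as its most stringent blinded test. CAFAS does not supply the missing power basis, however, as the pilot table has no effect size for it.
- **The one-sample basis is not specific to CGI-I.** It affects every Aim 1 and 2 outcome. Only the change to a binary endpoint is particular to this one.
- **The test is not named.** Aim 2 is to mirror Aim 1, which uses linear mixed models with covariates, and no model is given for the binary variable. A two-proportion calculation approximates whatever is eventually fitted.

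These points limit the size of the problem. None of them makes d = 2.81 a valid basis for the responder comparison.

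**Conclusion.** The point holds. The 0.80 power claimed for Hyp 2a does not apply to the planned test, because it rests on a single-arm mean change whereas the test compares responder rates between arms. Whether power is adequate depends on an ACC rate that the documents do not give: over the assumed 20% to 50%, it runs from over 0.99 down to 0.33 with 40 per arm, and from 0.97 down to 0.26 with 30.

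These figures assume two-sided 0.05, an unadjusted comparison of two proportions, and an EASE rate of 67% taken from 12 participants. They precede the Hochberg adjustment planned for Aims 1 to 3, which can only lower them. Both adequate and inadequate power are compatible with the documents. What needs correcting is the power statement, not the endpoint or the enrolment target.

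**What to change.** In the justification of sample size:

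- Remove CGI-I from the d-based range and average. The low end stays at 4 because of RSQ, and the average on the plan's own one-sample basis becomes (17 + 4 + 13 + 15 + 49)/5 = 19.6.
- State Hyp 2a power as a difference in responder rates, at 40 and 30 per arm, over ACC rates of 20% to 50%. Say that it is nominal (before Hochberg) and that the EASE rate comes from 12 pilot participants.
- Correct the one-sample basis for the whole sizing paragraph, since it affects all Aim 1 and 2 outcomes.

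Keep the responder endpoint in the Aim 2 analysis. A proportional-odds analysis of the full 7-point CGI-I is optional; it would not repair the power statement and is not part of this correction.

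The cost is a text change. Enrolment, visits and data collection are unaffected. The stated power for Hyp 2a becomes less favourable, and explicitly conditional on the control rate.

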#### **Aim 3: Examine the trajectory of change including the degree to which effects are sustained after treatment completion.**

The goal of Aim 3 is to test whether treatment effects persist over time even after the treatment ended, and to ensure they do not return to pre-treatment levels. The hypotheses in Aim 3, similar to the hypotheses in Aims 1 and 2, will be tested with linear mixed-effects models to determine whether the differential treatment effects are maintained once the 3-month follow-up time point is included (Hyp 3a). In addition, we will utilize HLM to evaluate the sustaining effects after the intervention (Aim 3) by estimating the differential trajectories of change between patients treated with EASE and ACC controls, with an emphasis for Hyp 3b on demonstrating sustained improvements over baseline.

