### **Aim 3 (Durability): Examine the trajectory of change including the degree to which effects are sustained after treatment completion.**

- ❑ H3a: Participants in the EASE group will maintain significantly greater gains in ER ability, functioning, and reduced psychiatric symptoms, and at 3-months post-treatment follow-up compared to ACC group.

- ❑ H3b: ER impairment will not return to pre-treatment levels three months after treatment completion.

[figure not shown]

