### **Statistical Analyses by Aim**

#### **Aim 1 (Primary Outcome): Show that EASE improves emotion regulation.**

First, to test the main effects of EASE on impaired ER (Hyp 1a) and maladaptive ER strategy use (Hyp 1b), we will employ linear mixed-effects models, with an auto-regressive error structure most appropriate to longitudinal data, allowing model intercepts and longitudinal trajectories to vary across subjects. Significant treatment by time interactions showing differences in linear rates of change in EDI Reactivity (Hyp 1a) and RSQ Involuntary and Voluntary Engagement scores (Hyp 1b) will be the effects of interest in these models. All mixed-effects models will control for potential demographic and medication confounds by including age, gender, IQ, and medication information as model covariates. This will be followed by modeling of growth trajectories between groups via HLM, also controlling for relevant potential confounds, using weekly data for Hyp 1a (EDI), and pre, mid, and post-treatment data for Hyp 1b (RSQ).

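### Hyp 3a claims an arm difference at 3 months, but no follow-up contrast is named and the test, read through its cross-reference, is a whole-period slope

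*Combined protocol and SAP*

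**What the plan says.** Section 1H (Aim 3) states Hyp 3a as a comparison at one time: EASE participants "will maintain significantly greater gains in ER ability, functioning, and reduced psychiatric symptoms, and at 3-months post-treatment follow-up compared to ACC group".

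Under Statistical Analyses by Aim, the Aim 3 paragraph says: "The hypotheses in Aim 3, similar to the hypotheses in Aims 1 and 2, will be tested with linear mixed-effects models". The purpose is to see "whether the differential treatment effects are maintained once the 3-month follow-up time point is included (Hyp 3a"). A second analysis, by HLM, compares the arms' trajectories and puts its emphasis for Hyp 3b on improvement over baseline.

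The Aim 1 paragraph defines what those models test: "Significant treatment by time interactions showing differences in linear rates of change". It gives the first-step mixed model random intercepts and trajectories, "with an auto-regressive error structure most appropriate to longitudinal data". The growth models by HLM come next, "using weekly data for Hyp 1a (EDI), and pre, mid, and post-treatment data for Hyp 1b (RSQ").

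The section on study variables places the main assessments at baseline, 8 weeks, 16 weeks and 3 months after treatment, with the parent EDI weekly. Nowhere does the plan name a contrast at the 3-month visit, a post-treatment segment, or what counts as maintained.

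**The concern.** A difference in linear slopes over the whole study and an arm difference at the last visit are different quantities. They agree only if the benefit keeps growing in a straight line to follow-up. Durability is in doubt precisely because it may not: the plausible shapes are improvement to week 16 followed by a plateau or a relapse.

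The mismatch matters most where many in-treatment points share one line with a single follow-up point, as could happen with the weekly parent EDI. The line is then driven mainly by the treatment phase, and a significant slope could be read as durability after the benefit has gone.

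The section on experiment-wise error treats Aim 3 as confirmatory and includes it in the Hochberg correction, so its contrast should be fixed in advance.

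**Working it through.** **Inputs from the plan.** Assessments at weeks 0, 8, 16 and 3 months later; weekly EDI; 80 participants allocated equally, so 40 per arm, or 30 per arm after the stated 25% attrition. The pilot EDI change reproduces: 0.49 / 0.67 = 0.73. The plan gives no power figure for Aim 3.

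**Assumptions.** Follow-up at week 29; week-16 arm effect d = 0.73; two-sided alpha 0.05 (2.5% in favour of EASE) before Hochberg adjustment; complete data. The benefit grows linearly to week 16 and is zero at week 29 (full relapse). The residual correlation is not given, so a range is used.

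**Step 1: slope on weekly EDI, weeks 0–16 plus 29, independent residuals.** With the arm difference y in units of the week-16 effect:
- Σt = 136 + 29 = 165; Σt² = 1496 + 841 = 2337; Sxx = 2337 − 165²/18 = 824.5.
- Σty = 1496/16 = 93.5; Σy = 136/16 = 8.5; Sxy = 93.5 − 165 × 8.5/18 = 15.58.
- Slope = 15.58/824.5 = 0.0189 per week. Over 29 weeks: 0.55 of the week-16 effect, when the true difference is 0.

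**Step 2: the same on weeks 0, 8, 16, 29.**
- Sxx = 1161 − 53²/4 = 458.75; Sxy = 20 − 53 × 1.5/4 = 0.125.
- Slope = 0.00027; over 29 weeks: 0.8% of the week-16 effect.

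**Step 3: other cases under full relapse.**

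| EDI data and residuals | Implied week-29 difference, % of week-16 effect |
|---|---|
| Weekly + 29, independent | 55% |
| Weekly + 29, AR in calendar time, 0.2 / 0.3 / 0.5 / 0.8 | 37% / 28% / 14% / 2% |
| Weekly + 29, AR by occasion, 0.2 / 0.3 / 0.5 / 0.6 | 31% / 16% / −22% / −47% |
| Weekly through week 29 (linear loss), independent | 9% |
| Weeks 0, 16, 29, independent | 7% |
| Weeks 0, 8, 16, 29, independent or AR in calendar time | about 1% (2% at 0.8) |

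**Step 4: chance of a significant slope favouring EASE, weekly + 29, independent residuals, full relapse, 40 per arm.** Var(slope) = random-slope variance + σ²/824.5; SE = √(2 Var/40); noncentrality = 0.73 × 0.0189/SE on 78 df.
- *d in units of the total SD* (baseline variance 1, σ² = 0.5, random-slope variance 0.05 to 0.4 over 16 weeks). At 0.05: Var = 0.05/256 + 0.5/824.5 = 0.00080, SE = 0.0063, noncentrality 2.18, probability 58%. At 0.4: Var = 0.00217, SE = 0.0104, noncentrality 1.32, probability 26%. So roughly 25% to 55%.
- *d in units of the SD of change*, as the pilot defines it, with random slopes supplying 20% to 80% of the change variance: noncentrality 1.73 to 1.08, probability 40% to 19% (31% to 15% with 30 per arm).
- On the four scheduled waves with independent residuals the probability is about 2.6%, essentially nominal.

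**Step 5: the direct contrast.** Testing the arm difference in change from baseline to week 29 holds the nominal 2.5% under full relapse. If the benefit is fully kept at d = 0.73 (SD-of-change scaling), its power is about 48% to 76% with 40 per arm and 38% to 63% with 30.

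**The case against.** A reader might infer that the plan prescribes a linear slope on weekly EDI for Hyp 3a and will therefore tend to declare durability falsely. The documents do not support that, for four reasons.

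- The Aim 3 paragraph does not itself say linear slope. It names a class of model and refers back to Aims 1 and 2. The general analytic approach calls the first-step models ANOVA mixed models, which is compatible with time as a category.
- Weekly data are assigned to the HLM, whereas Hyp 3a is attached to the first-step mixed model. If that model uses the four scheduled waves, the distortion is negligible with independent or calendar-time AR errors.
- The direction is not fixed. AR by occasion of 0.5 or more turns the weekly slope against EASE under relapse. Whether weekly EDI continues after week 16 is not stated; if it does, the distortion is small.
- A significant slope when a quarter of the benefit remains is not a false positive: a real difference exists, and Hyp 3a sets no retention margin.

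Hyp 3b is also a partial guard, since it would expose relapse in the EASE arm. It would not expose catch-up by the control arm and is not the between-arm test that Hyp 3a needs. RSQ is taken at the four main waves. The blind-rater and other-report EDI have only pre, post and follow-up, where the implied difference is about 7%.

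These points limit the size of the problem and where it applies. They do not supply the missing contrast: the same follow-up data could look durable, null or reversed depending on time coding, residual structure and schedule, none of which is settled for Aim 3.

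**Conclusion.** The point holds in conditional form. The hypothesis concerns the arm difference at 3 months; the test reached through the cross-reference is a whole-period slope, and no follow-up contrast is named.

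The serious case is an HLM on weekly EDI with a single follow-up point and independent residuals. Under full relapse the slope then implies about 55% of the week-16 benefit. It favours EASE in roughly 25% to 55% of trials, or 19% to 40% with d scaled to the SD of change, against a nominal 2.5%. These rates rest on d = 0.73, 40 per arm, week 29, the assumed variance splits, complete data and no Hochberg adjustment.

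The concern should not be extended to outcomes measured only at the main visits as a risk of falsely declared durability. It does not affect the Aim 1 test during treatment.

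**What to change.** In the Aim 3 analysis paragraph:
- Define Hyp 3a as the arm difference in change from baseline to the 3-month visit.
- Estimate it with time as a category, or piecewise linear with a knot at week 16, in both the mixed model and the HLM.
- State which EDI data enter each model and whether weekly collection continues after week 16.
- Report beside it the week-16 arm difference and the change from week 16 to follow-up in each arm.

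This is SAP wording only, using the same data and software. The direct contrast has limited power at this sample size (Step 5 of the working), so its confidence interval should be reported and a non-significant result should not be read as loss of benefit.
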